## **Background**

Accurately quantifying food intake is vital to promoting health and reducing chronic disease risk. Food intake encompasses energy intake, nutrient intake (macronutrients, micronutrients, vitamins, minerals), and intake of various food groups (e.g., fruits, vegetables), and thus reflects the nutritional status of individuals. Nutrition affects disease risk, including risk of developing obesity, diabetes, and cancer, all of which negatively affect the United States (U.S). Nonetheless, accurate assessment of food and nutrient intake has remained challenging, despite an improvement in methods. Self-report methods, namely food records, are a mainstay of nutritional epidemiology research, with food recall being another popular method. These methods rely on the participant to accurately estimate portion size and, for food recall, remember what was consumed. The accuracy of these methods have been questioned and the problems with human recall have been comprehensively outlined. As a result, there remains a significant need for methods that are sufficiently accurate to provide researchers with good outcome data and to guide health promotion efforts.

The PortionSize™ app was designed by our laboratory to overcome the limitations outlined above, and to guide users to follow specific diets. PortionSize™ relies on users capturing images of their food selection and waste. Food intake data are immediately provided since the user relies on built in tools, including templates, to estimate portion size. However, despite promising early indications, the PortionSize™ app has yet to be validated. Determining the accuracy and reliability of PortionSize™ is vital before the app can be used by people to obtain immediate feedback about their food intake. We accordingly aim to test the reliability and validity of PortionSize™ in a semi-controlled free-living environment using food provision. We will also test the reliability and validity of the MyFitnessPal app in a semi-controlled free-living environment. The accuracy of the apps will also be compared to each other.

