### ***Baseline (and Day 0)***

Participants will attend an in-person visit at Pennington for Baseline, which occurs during Period 1, to be randomized and trained how to use the app that they will use first. During Day 0, which occurs during Period 2, participants will be trained to use the app that they will use second. These visits will last ~45 to 60 minutes. The training will teach participants how to report food intake and estimate portion size per our standard procedures. Participants will receive training by study staff members on the app that they will use for that period. That is, individuals randomized to use PortionSize™ first will be trained on PortionSize™, whereas those randomized to use MyFitnessPal first will be trained on MyFitnessPal. This first day is usually a partial day of data collection and will serve as a run-in/familiarization period for the participants, during which they will be instructed to use the app for the remainder of the day. These data will not be analyzed as part of the 3-day use period.

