### Outcome measures

The **primary analyses** assessing equivalence between PortionSize™ and the criterion measure (and MyFitnessPal and the criterion measures) will rely on equivalence testing using the Two One-side T-test (TOST) method. The null hypothesis of an equivalence tests is that the means are nonequivalent, i.e., the confidence interval of the mean of the test condition exceeds the pre-specified error bound. The alternative hypothesis is that the means are equivalent, and the mean difference between the experimental method and gold standard is hypothesized to be zero. Differences in error from PortionSize™ compared to error from MyFitnessPal will be assessed using dependent samples t-tests, with error calculated as the difference between each experimental method and the criterion variable (e.g., energy intake values from PortionSize™ minus energy intake values from weighed foods). These procedures will also produce results indicating if the error from each method differs from zero.

Subsequent regression-based **exploratory analyses** will determine if error from the apps varies by body mass (kg, BMI), age, or sex; and will evaluate differences in user satisfaction between the apps. Bland-Altman analysis will be used to test for differences in error variance over levels of the variable being measured (e.g., food intake).

Endpoints will be:

- Energy intake (kcal)
- User satisfaction and usability of the apps
- Nutrients (e.g., fat, carbohydrate, and protein as grams and percent energy from each macronutrient) and food groups (PortionSize™ only since it has the ability to provide output in food groups due to the link with the FNDDS database).

Other exploratory endpoints include human rater analysis of captured food images and the modified Dietary History Questionnaire III (DHQIII) as comparators for food and possible dietary supplement intake.

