### Power calculation

We expect no more than ~8% drop-out and will recruit at least 45 participants; hence, power analyses were conducted with a sample size of at least 42.

Estimated food intake values from the PortionSize™ and MyFitnessPal apps will be compared to directly weighed values, which serve as the criterion measure. Equivalence tests that follow the Two One-sided T-test (TOST) method will be used

(error reflects the difference between weighed intake and estimates from either PortionSize or MyFitnessPal). Based on a new power analysis and variance estimates from a recently completed pilot study, equivalence is set as within  $\pm$  17.9% of the directly weighed value. The power assumed: 42 participants, energy (kcal) intake as the outcome variable, alpha = 0.05, power  $>0.80$  as acceptable, and mean weighed intake = 2,360 kcal with an SD (difference) = 917 kcal. We will also test for equivalence at the original bound of  $\pm$  9%, as well as a new bound of  $\pm$  14%, though we recognize that these tests will likely be underpowered. Finally, with at least 42 participants completing the PortionSize and MyFitnessPal condition, we have 0.80 power to detect an R^2 of 0.17, which is acceptable as studies with Bland-Altman analysis find that poor methods of measurement frequently have R^2  $>0.16$ .

With 42 participants in each group, power is limited for the tests to examine differences in error between PortionSize™ and MyFitnessPal; therefore, these comparisons are exploratory.

The reliability of each apps' food intake estimates will be quantified with intraclass correlation coefficients (ICCs), and reliability will be supported if the ICC is significant and  $\geq 0.50$ . A power analysis indicates that, with 2 observations per subject, an ICC of 0.54 can be detected with 23 subjects at 80% power. The power analysis was conducted in R software using the 'ICC.Sample.Size' package based on Zou. Regression-based exploratory analyses are powered to detect an R^2 of 0.127 and thus have ample power.

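### The only between-app test of intake compares mean bias; it cannot see a difference in error spread and needs an absolute-error and a spread comparison beside it

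*Combined protocol and SAP*

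**What the plan says.** All references are to the combined protocol and SAP.

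- **Aim.** Background: "The accuracy of the apps will also be compared to each other".
- **Test.** Outcome measures: "Differences in error from PortionSize™ compared to error from MyFitnessPal will be assessed using dependent samples t-tests". The same section then defines the quantity that is compared: "with error calculated as the difference between each experimental method and the criterion variable". The worked example there is a plain subtraction, "energy intake values from PortionSize™ minus energy intake values from weighed foods", so the error keeps its sign.
- **Status.** Power calculation notes that power for this comparison is limited; "therefore, these comparisons are exploratory".
- **Per-app results.** Each app has its own equivalence test (TOST) against weighed intake. Outcome measures adds: "These procedures will also produce results indicating if the error from each method differs from zero". Power calculation adds an intraclass correlation for each app.
- **Spread.** A Bland-Altman analysis "will be used to test for differences in error variance over levels of the variable being measured". This looks at how error varies with intake, not at one app against the other.
- **Unit.** Baseline (and Day 0) says of the run-in day: "These data will not be analyzed as part of the 3-day use period". No section states whether error is taken per day or over the three days.

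No section defines absolute error or plans a between-app test of error spread.

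**The concern.** Accuracy has two parts: how far the average estimate is from weighed intake (bias), and how widely individual estimates scatter (spread). A paired t-test on signed error addresses only the first. This leaves two gaps.

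1. If both apps have the same mean bias but one is far more erratic, the test has nothing to detect. A non-significant result could then be read as similar accuracy.
2. If one app over-reports and the other under-reports by the same amount with equal spread, the test tends to reject although neither app is closer to the truth.

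The signed test does point to the less accurate app when both err in the same direction with similar spread, so it is useful but incomplete. At stake is what can be said about the stated aim of comparing the apps' accuracy, because no other planned analysis tests one app's closeness or spread against the other's.

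**Working it through.** **Inputs from Power calculation:** n = 42, alpha = 0.05, mean weighed intake 2,360 kcal, SD of the difference 917 kcal, margin ±17.9%.

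**Assumptions, not in the documents:** normal errors; the true biases; the second app's SD; a correlation ρ of 0 to 0.7 between the two apps' errors; 917 kcal applies to the per-participant error analysed; two-sided 0.05 for between-app tests.

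**Step 1. The plan's own figure.** Margin = 0.179 × 2,360 = 422.4 kcal. SE = 917/√42 = 141.5 kcal. With a true difference of zero, TOST power by the normal approximation is 2Φ(422.4/141.5 − 1.645) − 1 = 0.820. The t version gives 0.803. The stated power above 0.80 is reproduced, so the inputs are being read as the plan intends.

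**Step 2. What the signed test can detect.** The SD of the within-person difference in errors is 917√(2(1 − ρ)). The difference in mean bias detectable with 80% power is 574, 480, 406 or 314 kcal at ρ = 0, 0.3, 0.5 or 0.7. This agrees with the plan's remark that power is limited.

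**Step 3. Mean absolute error.** For bias μ and SD σ, E|e| = σ√(2/π)·exp(−μ²/2σ²) + |μ|(1 − 2Φ(−|μ|/σ)).

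- No bias: 732 kcal at SD 917; 366 kcal at SD 458.5.
- Bias of −236 or +236 kcal (10% of 2,360), SD 917: 756 kcal each.
- Bias of −118 kcal (5%) and −472 kcal (20%), SD 917: 738 and 826 kcal.

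**Step 4. Rejection rates.** When biases differ, the signed test is exact by the noncentral t with 41 df and noncentrality Δ/(917√(2(1 − ρ))/√42).

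- Opposite biases, Δ = 472: 472/200.1 = 2.36 at ρ = 0 (power 63%); 472/109.6 = 4.31 at ρ = 0.7 (99%).
- Same direction, Δ = 472 − 118 = 354: 1.77 (41%) and 3.23 (88%).

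The other rates come from simulation, 200,000 trials per cell. Absolute error uses a paired t-test on |e₁| − |e₂|. Pitman-Morgan tests the correlation r of e₁ + e₂ with e₁ − e₂, t = r√(40/(1 − r²)), 40 df. Ranges run over ρ = 0 to 0.7.

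| Biases; SDs (kcal) | Signed | Absolute | Pitman-Morgan |
|---|---|---|---|
| 0, 0; 917, 458.5 | 5% | 98% to 99.9% | 99% or more |
| −472, −472; 917, 458.5 | 5% | 71% to 94% | 99% or more |
| 0, 0; 917, 687.75 | 5% | 38% to 61% | 44% to 71% |
| −472, −472; 917, 687.75 | 5% | 23% to 43% | 44% to 71% |
| −236, +236; 917, 917 | 63% to 99% | 5% | 5% |
| −118, −472; 917, 917 | 41% to 88% | 10% to 14% | 5% |

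In the first two rows a signed-rank test on absolute error gives 95% to 99.7% and 61% to 89%. The last row shows why absolute error cannot replace the signed test.

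**Step 5. Unit.** With three complete days, the mean of the daily signed errors in kcal equals the signed error of the 3-day mean, so the planned test in kcal is the same either way. Absolute error is not. Take 917 kcal as the SD of the 3-day mean and a day-to-day error correlation of 0.3 to 0.7 (assumed). The daily SD is 917/√((1 + 2 × 0.3)/3) = 1,256 kcal, or 1,025 kcal at 0.7. Mean absolute error is then 732 kcal on the 3-day mean but 1,002 to 818 kcal per day. An absolute-error test on the 3-day mean would reject only 5% between two such apps, because daily over- and under-reporting cancel.

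**The case against.** Three objections carry weight.

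**The opposite-bias case is mostly visible already.** Each app's mean error is tested against zero and by its own TOST. In the −10%/+10% scenario, when the signed test is significant, the two observed mean errors have opposite signs in 91% to 99% of trials, so a reader would see one app over-reporting and the other under-reporting. This largely stands. The remaining risk lies in reading significance labels alone: in about 62% to 66% of those trials exactly one of the two equally inaccurate apps is flagged as different from zero. A reader might infer that the plan will name the wrong app as more accurate, but no section says the signed test will be used to name one.

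**The unspecified unit does not damage the planned test.** A reader might infer that the signed comparison is undefined. With complete days it is the same in kcal under either reading; the unit matters for an added absolute-error measure, or if days are missing or entered as separate rows.

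**A comparison of mean bias is legitimate, is labelled exploratory, and nothing in the documents points to a twofold difference in SD.** All true. At a 25% smaller spread the added tests have only low to moderate power. But exploratory status does not change what the test measures, and nothing planned fills the spread gap: the TOSTs, error-versus-zero tests and intraclass correlations are per app, and Bland-Altman looks across intake levels.

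**Conclusion.** The point holds and is minor. The planned between-app test compares mean bias only. It stays at about 5% however much the error spreads differ when biases are equal, while an absolute-error test would detect a halving of spread in 71% to 99.9% of trials and Pitman-Morgan in 99% or more. For a 25% reduction the figures are 23% to 61% and 44% to 71%. For equal and opposite 10% biases it rejects 63% to 99%, so its result must be read beside the per-app mean errors. These rates rest on the plan's n and SD together with the assumed normal errors, biases, second SD and correlation of 0 to 0.7.

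Two stronger readings are not supported. The signed test should not be discarded: it is the more sensitive one when both apps err in the same direction with similar spread. And the primary TOSTs, their margins and the sample size are not affected, since each concerns one app against weighed intake.

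**What to change.** In Outcome measures:

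1. Keep the signed-error t-test and label it an exploratory comparison of mean bias, read together with each app's mean error.
2. Add one prespecified exploratory paired comparison of absolute error, |app − weighed|, in kcal and as a percentage of weighed intake, using a bootstrap or signed-rank test because absolute errors are skewed.
3. Add a paired comparison of error spread: Pitman-Morgan, or the two apps' limits of agreement side by side.
4. State the unit of absolute error in advance. The 3-day mean measures accuracy of average intake but lets daily errors cancel; the mean of daily absolute errors measures daily accuracy. Choose according to the claim to be made, and say how missing days are handled.
5. Base any statement about which app is more accurate on bias together with absolute error or spread.

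The cost is SAP wording and a derived variable, with no new data. The downsides are extra exploratory multiplicity, an absolute-error measure that mixes bias and spread, low to moderate power for modest spread differences, and Pitman-Morgan's reliance on normal errors and its blindness to bias.

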### ***Day 1***

Participants will return to the lab before breakfast in the morning to be weighed (non-metabolic) and be provided with the first cooler of food to consume for the remainder of the day. The coolers will contain about 1.3 times the participant's overall estimated energy needs, with ~20%, 30%, 40%, and 10% of energy provided as breakfast, lunch, dinner, and snacks, respectively. Staff will attempt to provide a day's worth of food that reflects 50% carbohydrate, 20% protein, and 30% fat (+/- 5%). The Mifflin St. Jeor Equation will be used to calculate basal metabolic rate (BMR), and total energy requirements will be calculated by multiplying BMR by an activity factor of 1.5. This value then will be multiplied by 1.3 to provide 30% more energy than the person requires. Participants will be instructed to only consume foods and beverages (with the

exception of water and non-caloric beverages such as black coffee or plain tea) from the cooler, but they can eat/drink as much or as little as they wish. Participants who report drinking diet, regular sodas, or sweet teas will be provided with their preferred beverage in their cooler, and efforts will be made to provide these beverages in typical store-bought containers (e.g., 12-ounce cans). All food and beverage items will be pre-weighed and weighed immediately upon return per our previous methods. We may include dietary supplement(s) on certain days, though the supplement may vary among participants (e.g., multivitamin, energy bar or shake, etc.).

This visit will last approximately 15-30 minutes.

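### The regressions of app error on body mass, age and sex appear to use kcal error; because food supplied is scaled to body size and sex, a uniform percentage bias can look like a modest weight or sex effect.

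*Combined protocol and SAP*

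**What the plan says.** Outcome measures (Combined protocol and SAP) introduces error in the comparison of the two apps, "with error calculated as the difference between each experimental method and the criterion variable", with the example "energy intake values from PortionSize™ minus energy intake values from weighed foods". Power calculation repeats the idea: "error reflects the difference between weighed intake and estimates from either PortionSize or MyFitnessPal". Both are raw differences, and the energy endpoint is in kcal.

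The next paragraph of Outcome measures says that exploratory regressions "will determine if error from the apps varies by body mass (kg, BMI), age, or sex". It gives no unit, percentage error, log ratio or adjustment for weighed intake. A Bland-Altman analysis of error variance over the level of intake is listed separately.

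On food supply, the Day 1 section states "The coolers will contain about 1.3 times the participant's overall estimated energy needs" and, for the basis of those needs, "The Mifflin St. Jeor Equation will be used to calculate basal metabolic rate (BMR), and total energy requirements will be calculated" by applying an activity factor of 1.5. The cooler is meant to be the only caloric source, but the amount eaten is left to the participant. Participants and Recruitment spreads enrolment over three BMI bands from 18.5 to 50 and about equal numbers of men and women.

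**The concern.** Supply is built from the same variables that are later tested as moderators. If larger people and men eat more because they need more and are given more, an app that misses the same percentage for everyone misses more kcal in those groups. A regression of kcal error on weight or sex then has a non-zero slope with no difference in relative accuracy.

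At stake is the reading of the only planned analyses that ask whether the apps work less well in some kinds of user. A slope that reflects how much was eaten could be reported as poorer accuracy in heavier or male users. The same holds for nutrients in grams, but not for percent energy from macronutrients.

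**Working it through.** **Inputs from Power calculation:** n = 42, mean weighed intake 2,360 kcal, SD of difference 917 kcal, equivalence bound ±17.9%, alpha 0.05. **From Day 1:** supply = BMR × 1.5 × 1.3 = 1.95 × BMR. **Assumed:** usual coefficients of the named BMR equation, heights of 163 cm (woman) and 176 cm (man), and intake centred on estimated need.

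**1. The plan's own figure.** Margin = 0.179 × 2,360 = 422.4 kcal. SE = 917/√42 = 141.5 kcal. TOST power at zero true difference, 0.05 per side = 2Φ(422.4/141.5 − 1.645) − 1 = 0.82 (0.803 with t). The stated power above 0.80 reproduces, so these planning values can be used below.

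**2. Size of the kcal artefact without the BMR equation.** Take intakes 25% below and above the mean: 1,770 and 2,950 kcal.
- Uniform −10%: −177 vs −295 kcal, 118 apart.
- Uniform −17.9%: −317 vs −528 kcal, 211 apart.

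**3. Size with the BMR equation.** Estimated needs (1.5 × BMR), with intake set equal to need and a uniform −17.9% error:

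| Contrast | Needs (kcal) | Difference | × 0.179 |
|---|---|---|---|
| Man vs woman, BMI 27.5, age 40 | 2,635 vs 2,083 | 552 | 99 kcal |
| Woman, BMI 40 vs 21.75, age 40 | 2,581 vs 1,853 | 728 | 130 kcal |
| Man, BMI 27.5, age 18 vs 62 | 2,800 vs 2,470 | 330 | 59 kcal |

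The age contrast spans the whole eligible range and is still the smallest.

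**4. Against the plan's noise.** With 21 men and 21 women, the SE of a difference in mean kcal error is 917 × √(2/21) = 283 kcal. A false gap of 99 kcal is 99/283 = 0.35 SE. The two-sided rejection rate is about Φ(−1.96 + 0.35) + Φ(−1.96 − 0.35) = 0.054 + 0.010 = 6.4%, against a nominal 5%.

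**5. Simulation.** n = 42, 1,500 trials per setting, percentage error independent of all covariates, intake proportional to need with 15% individual variation, uniform bias −17.9%. Rejection rates at 0.05:

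| SD of percentage error | SD of kcal error | kcal: weight | kcal: sex | kcal: age | Percentage error: weight, sex, age |
|---|---|---|---|---|---|
| 10% | 264 | 39% | 23% | 7% | 4% to 5% |
| 20% | 495 | 18% | 10% | 5% | 5% |
| 38% | 921 | 10% | 6% | 5% | 5% |

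The last row matches the plan's 917 kcal (917/2,360 = 38.9%). Repeat simulations under similar assumptions give 10% to 11% for weight, about 7% for sex and 5% to 6% for age. The false male-female gap is 96 to 110 kcal at every SD. At −10% bias and 38% SD it is about 57 kcal.

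With zero average bias, rejection for weight is still about 7% to 9%, because the variance of kcal error grows with intake. At the plan's SD, part of the excess over 5% therefore comes from unequal variance and the rest from the bias.

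**6. The reverse case.** If the error is instead a constant −472 kcal (20% of 2,360) with SD 400, kcal error rejects at 5%, but percentage error rejects in 18% to 19% of trials for weight and 13% to 14% for sex. At −708 kcal (30%) percentage error rejects in 37% and 22%. Kcal error with weighed intake as a covariate stays at 5% to 7% under both the proportional and the constant error.

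**The case against.** - **The unit is inferred.** The definition of error sits in the sentence on the app-versus-app comparison, and the regression sentence names no scale. This stands as a limit on wording. But the plan offers no other definition, and Power calculation repeats the raw difference.
- **The inflation is small at the plan's SD.** This stands. A reader might infer false-positive rates of 25% to 45%, or a 300 kcal false effect. Those rates need individual percentage error far less variable than the plan assumes, together with a bias of 20% to 30%, outside the ±17.9% bound. A 300 kcal gap needs a contrast such as a small 60-year-old woman against a 110 kg, 25-year-old man.
- **Intake is ad libitum.** This stands: the design fixes supply, not intake, so the artefact is not certain. It is still likely that intake rises with estimated need.
- **The plan hypothesises a zero mean difference.** At zero bias there is no false slope in the mean. But the trial exists because the bias is unknown, and a non-zero bias inside the bound is enough.
- **Bland-Altman covers it.** That analysis could reveal error that grows with intake and so give context. It does not adjust the moderator regressions.
- **Percentage error has its own flaw.** This stands, as step 6 shows. The documents do not say whether error is proportional or constant, so they do not support replacing one scale with the other.

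**Conclusion.** The point holds at a modest size. On the natural reading, the moderator regressions use raw kcal error while food supply is scaled to the moderators. With a uniform −17.9% bias and the plan's SD, the false-positive rate is about 10% for weight, about 7% for sex and near 5% for age, with a false male-female gap of about 100 kcal. The gap does not shrink as individual error becomes less variable; it only becomes easier to declare significant.

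This rests on intake following estimated need, non-zero average bias, error that is proportional to intake, and assumed heights, BMI spread and BMR coefficients.

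Two stronger readings are not supported. A reader might infer a material false age effect, but the simulated rate at the plan's SD is close to nominal. A reader might also infer that the equivalence result is compromised. The regressions are labelled exploratory, and the primary TOST and its sample size do not depend on them.

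**What to change.** Add to Outcome measures that the body mass, age and sex regressions will be run either
- on percentage error, 100 × (app − weighed)/weighed, computed on each participant's mean over the analysed days and reported beside kcal error; or
- on kcal error with weighed intake as a covariate.

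State also that a moderator effect seen only in unadjusted kcal will not be read as lower accuracy in that group.

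The cost is a sentence or two in the analysis text, no new data, and one extra set of exploratory results. Percentage error gives more weight to low-intake participants and can itself mislead if the error is a constant number of kcal, so it should stand beside kcal error and not replace it.
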